2.6.6 Supplementary analyses

No supplementary analysis is planned for the secondary (efficacy) estimands.

2.7 Safety analyses

For all safety analyses, the Safety Set will be used.

Safety summaries (tables, figures) include only data from the on-treatment period with the exception of baseline data which will also be summarized where appropriate (e.g., change from baseline summaries).

For details of the on-treatment period, please see Section 2.1.1.3.

2.7.1 Adverse events (AEs)

See Section 2.5.

| Novartis | Confidential | Page 39 of 54 |
|----------|--------------|------------------------|
| SAP | | Study No. CLOU064A1301 |

2.7.1.1 Adverse events of special interest / grouping of AEs

See Section 2.5.2.

2.7.1.2 Requirements of ClinicalTrials.gov

For the legal requirements of ClinicalTrials.gov, two required tables on treatment emergent adverse events (AEs): non-serious AEs with an incidence greater than 5%, and deaths and serious AEs (SAEs) including the events suspected to be related to study treatment, will be provided by system organ class (SOC) and preferred term (PT) on the Safety Set. The cut-off of 5% can be re-evaluated based on number of participants with events.

If for a same participant, several consecutive AEs (irrespective of study treatment causality, seriousness and severity) occurred with the same SOC and PT:

- a single occurrence will be counted if there is ≤ 1 day gap between the end date of the preceding AE and the start date of the consecutive AE
- more than one occurrence will be counted if there is > 1 day gap between the end date of the preceding AE and the start date of the consecutive AE

For occurrence, the presence of at least one SAE / SAE suspected to be related to study treatment / non-SAE has to be checked in a block e.g., among AEs in $a \le 1$ day gap block, if at least one SAE is occurring, then one occurrence is calculated for that SAE.

The number of deaths resulting from SAEs suspected to be related to study treatment and SAEs irrespective of study treatment relationship will be provided by SOC and PT.

These tables will be provided at the final analysis after completion of the study.

2.7.2 Deaths

Death including on-treatment and post-treatment deaths will be listed.

2.7.3 Laboratory data

All laboratory data will be listed by participant and visit and if normal ranges are available abnormalities will be flagged.

For Hematology and Serum chemistry, central laboratory data will be included in the summary tables. Local laboratory data will only be listed but not be included in the summary tables.

For Urinalysis, local laboratory data will be included in the summary tables. For participants who have only central laboratory data, central data will be used in the summary tables. Both of local and central data will be listed. For by-visit summary tables, scheduled visits (including remapped visits following the assessment window in Section 2.1.1.4) will be considered in the analysis. Unscheduled visits will not be included.

For notable summary tables, all post-baseline visits including unscheduled visits will be considered in the analysis.

The summary of laboratory evaluations will be presented for three groups of laboratory tests (Hematology, Serum chemistry and Urinalysis).

| Novartis | Confidential | Page 40 of 54 |
|----------|--------------|------------------------|
| SAP | | Study No. CLOU064A1301 |

For continuous variables, descriptive summary statistics for the change from baseline to each study visit will be presented. These descriptive summaries will be presented by laboratory test. Change from baseline will only be summarized for participants with both baseline and post baseline values and will be calculated as:

change from baseline = post baseline value – baseline value.

For categorical variables, descriptive statistics will be presented in contingency tables including the number and percentage of participants for each category.

For Hematology and Serum chemistry, the maximum change from baseline (maximum decrease and maximum increase) will be summarized during the treatment period.

In addition, for laboratory parameters where normal ranges are available, shift tables will be provided for all parameters to compare a participant's baseline laboratory evaluation relative to the worst on-treatment value. For the shift tables, the normal laboratory ranges will be used to evaluate whether a particular laboratory test value was normal, low, or high for each visit value relative to whether or not the baseline value was normal, low, or high. These summaries will be presented by laboratory test.

The following laboratory parameters will be analyzed with respect to numerical Common Terminology Criteria for Adverse Event (CTCAE) grades (version 5.0), given in Table 2-8: hemoglobin, platelets, white blood cells, neutrophils, lymphocytes, prothrombin time-international normalized ratio (INR), creatinine, creatinine kinase, total bilirubin (TBL), gamma-glutamyl transferase (GGT), alanine aminotransferase (ALT), aspartate aminotransferase (AST), alkaline phosphatase (ALP), total cholesterol, triglycerides, amylase, and lipase.

CTCAE grades based on lab results alone will be applied programmatically, and clinical assessments (in *italic* below) will not be considered. In case of missing baseline laboratory assessment, it will be assumed as normal. The number and percentage of participants with CTCAE grade newly occurring or worsening after baseline will be presented. A case is considered as newly occurring abnormality if the value is not notable or missing at baseline but is notable thereafter. A case is considered as worsening abnormality if the value is notable at baseline and at least one post-baseline value is worse than baseline.

Shift tables will be provided on CTCAE grades to compare baseline relative to the worst grade. These summaries will be split into hematology and chemistry, and will be presented.

| CTCAE term | Laboratory assessment | Grade 1 | Grade 2 | Grade 3 | Grade 4 |
|--------------------------|--------------------------|--|------------------------------------|------------------------------------|-------------------------------|
| Anemia | Hemoglobin (Hgb) | <lln-10.0 g/dL</lln-10.0 | <10.0-8.0 g/dL | <8.0 g/dL | Life-threatening consequences |
| Platelet count decreased | Platelets | <lln- 75,000/mm³</lln- | <75,000- 50,000/mm ³ | <50,000- 25,000/mm ³ | <25,000/mm ³ |

 Table 2-8
 CTCAE grades for laboratory parameters to be analyzed

| White blood cell count decreased | White blood cells | <lln- 3000/mm³</lln- | <3000- 2000/mm ³ | <2000- 1000/mm ³ | <1000/mm ³ |
|--|--|--|--------------------------------|--------------------------------|-----------------------|
| Neutrophil count decreased | Neutrophils | <2000- 1500/mm ³ | <1500- 1000/mm ³ | <1000-500/mm ³ | <500/mm ³ |
| Lymphocyte count decreased | Lymphocytes | <1500-800/mm ³ | <800-500/mm ³ | <500-200/mm ³ | <200/mm ³ |
| INR increased | INR | >1.2-1.5 | >1.5-2.5 | >2.5 | - |
| Creatinine increased | Serum creatinine | >ULN-1.5 x ULN | >1.5-3.0 x ULN | >3.0-6.0 x ULN | >6.0 x ULN |
| Creatinine kinase increased | Serum creatinine kinase | >ULN-2.5 x ULN | >2.5 - 5.0 x ULN | >5.0 - 10.0 x ULN | >10.0 x ULN |
| Blood bilirubin increased | Total bilirubin (TBL) | >ULN-1.5 x ULN | >1.5-3.0 x ULN | >3.0-10.0 x ULN | >10.0 x ULN |
| GGT increased | Gamma- glutamyl transferase (GGT) | >ULN-2.5 x ULN | >2.5-5.0 x ULN | >5.0-20.0 x ULN | >20.0 x ULN |
| ALT increased | Alanine aminotransfera se (ALT) | >ULN-3.0 x ULN | >3.0-5.0 x ULN | >5.0-20.0 x ULN | >20.0 x ULN |
| AST increased | Aspartate aminotransfera se (AST) | >ULN-3.0 x ULN | >3.0-5.0 x ULN | >5.0-20.0 x ULN | >20.0 x ULN |
| ALP increased | Alkaline phosphatase (ALP) | >ULN-2.5 x ULN | >2.5-5.0 x ULN | >5.0-20.0 x ULN | >20.0 x ULN |
| Total cholesterol increased | Total Cholesterol | >ULN-7.75 mmol/L | >7.75-10.34 mmol/L | >10.34-12.92 mmol/L | >12.92 mmol/L |
| Triglyceride increased | Triglyceride | >=1.71-3.42 mmol/L | >3.42-5.7 mmol/L | >5.7-11.4 mmol/L | >11.4 mmol/L |
| Amylase increased | Amylase | >ULN-1.5 x ULN | >1.5-2.0 x ULN | >2.0-5.0 x ULN | >5.0 x ULN |
| Lipase increased | Lipase | >ULN-1.5 x ULN | >1.5-2.0 x ULN | >2.0-5.0 x ULN | >5.0 x ULN |

ULN: Upper limit of normal range; LLN: Lower limit of normal range.

Note: The comparison with baseline is not considered for derivation of LAB CTC grade due to Novartis CTCAE V5 implementation guide.

| Novartis | Confidential | Page 42 of 54 |
|----------|--------------|------------------------|
| SAP | | Study No. CLOU064A1301 |

To evaluate potential drug-induced liver injury, newly occurring liver enzyme abnormalities will also be summarized based on the event criteria given in Table 2-9. For the combination criteria of parameters, except potential Hy's Law case, all the elevations must occur at the same post-baseline timepoint. A case will be considered as newly occurring if a criterion is not met or missing at baseline but is met thereafter. A case is considered as worsening abnormality if the value is notable at baseline and at least one post-baseline value is worse than baseline.

Similarly, participants meeting specific renal alert criteria at any post-baseline will be summarized according to Table 2-10.

In addition to liver enzyme test abnormalities, for participants meeting the criteria [ALT or AST >5x ULN] or [ALT or AST>3xULN & TBL >2xULN & ALP <2xULN], graphical case (per participant) representation to include graph of liver enzymes over time (ALT, AST, TBL, ALP, based on xULN) with treatment exposure and concomitant medications, will be provided if any case.

Table 2-9Liver enzyme abnormalities

| | · · · · · · · · · · · · · · · · · · · |
|--------------------------|--|
| Parameter | Criterion |
| ALT | >3xULN; >5xULN; >8xULN; >10xULN; >20xULN |
| ALT or AST | >3xULN; >5xULN; >8xULN; >10xULN; >20xULN |
| (ALT or AST) & TBL | >3xULN & (TBL>1.5xULN; >2xULN) |
| (ALT or AST) & INR | >3xULN & INR>1.5 |
| TBL | >1xULN; >1.5xULN; >2xULN |
| ALP | >1.5xULN; >2xULN; >5xULN |
| ALP & TBL | >3xULN; >5xULN & TBL>2xULN |
| (ALT or AST) & TBL & ALP | ALT or AST>3xULN & TBL>2xULN & ALP<2xULN (Potential Hy's Law) |

Table 2-10 Specific renal alert criteria

| Parameter | Notable criteria |
|-----------------------------------|---|
| Serum creatinine | Increase 25% - <50% (%change from baseline) |
| | Increase $\geq 50\%$ |
| Dipstick proteinuria | \geq 3 + (Newly occurring) |
| Dipstick hematuria (occult blood) | ≥ 3 + (Newly occurring) |

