# 8.4.1 Laboratory evaluations

A central laboratory will be used for analysis of all specimens detailed in this section (Table 8-9) unless noted otherwise. Details on the collections, shipment of samples and reporting of results by the central laboratory are provided to investigators in the laboratory manual.

If participants cannot visit the site for protocol specified safety lab assessments (per Section 4.6), an alternative lab (local) collection may be used.

Clinically notable laboratory findings are defined in Section 16.1.

Clinically significant abnormalities must be recorded on the relevant section of the eCRF capturing medical history/current medical conditions/AEs.

Table 8-9 Laboratory assessments

Table 6-3	Laboratory assessments
Test Category	Test Name
Hematology	Hematocrit, Hemoglobin, [in the case of clinically significant anemia the following parameters will be assessed: Ery. Mean Corpuscular Hemoglobin (MCH), Ery. Mean Corpuscular Hemoglobin Concentration (MCHC), Ery. Mean Corpuscular Volume (MCV)], Platelets, Erythrocytes, Leukocytes, and Differential (Basophils, Eosinophils, Lymphocytes, Monocytes, Neutrophils, Bands)
Chemistry	Albumin, Alkaline phosphatase (ALP), Alanine Aminotransferase (ALT), Aspartate Aminotransferase (AST), Gamma-glutamyl-transferase (GGT), Lactate dehydrogenase (LDH), Calcium, Magnesium, Phosphate, Chloride, Sodium, Potassium, Creatinine, Creatine Kinase (CK), Direct Bilirubin, Indirect Bilirubin (in case of clinically significant elevation), Total Bilirubin, Total Cholesterol, Low Density Lipoprotein (LDL) Cholesterol, High Density Lipoprotein (HDL) Cholesterol, Total Protein, Triglycerides, Urea Nitrogen or Urea, Uric Acid, Amylase, Lipase C-reactive protein (CRP), estimated Glomerular Filtration Rate (eGFR): in all patients at screening, baseline, Weeks 12, 24 and 52 and when deemed necessary by the investigator at any other visits than those listed. Fasting glucose assessed at baseline, Weeks 2, 12 and 52.
Urinalysis	Done on site: Macroscopic Panel (Dipstick) (Color, Bilirubin, Occult Blood, Macroscopic Blood, Glucose, Ketones, Leukocytes esterase, Nitrite, pH, Protein, Specific Gravity, Urobilinogen)
Coagulation	Prothrombin time (PT), International normalized ratio (INR), Activated partial thromboplastin time (APTT)

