# 10.2 Additional Safety Monitoring

## 10.2.1 Liver safety monitoring

To ensure participant safety and enhance reliability in determining the hepatotoxic potential of an investigational drug, a standardized process for identification, monitoring and evaluation of liver events has to be followed.

Please refer to Table 16-1 in Section 16.2 for complete definitions of liver laboratory triggers.

Once a participant is exposed to study treatment, every liver event defined in Table 16-1 should be followed up by the investigator or designated personnel at the trial site, as summarized below. Additional details on actions required in case of liver events are outlined in Table 16-2 and Table 16-3. Repeat liver chemistry tests (i.e., ALT, AST, TBL, PT/INR, ALP and GGT) to confirm elevation.

These liver chemistry repeats will be performed using the central laboratory. If results will not be available from the central laboratory, then the repeats can also be performed at a local laboratory to monitor the safety of the participant. If a liver event is subsequently reported, any local liver chemistry tests previously conducted that are associated with this event should have results recorded on the appropriate CRF.

- If the initial elevation is confirmed, close observation of the participant will be initiated, including consideration of treatment interruption if deemed appropriate.
- Discontinuation of the investigational drug (refer to Section 9.1 and Section 16.2), if appropriate
- Hospitalization of the participant if appropriate
- Causality assessment of the liver event
- Thorough follow-up of the liver event should include, based on investigator's discretion:
  - serology tests, imaging and pathology assessments, hepatologist's consultancy; obtaining more detailed history of symptoms and prior or concurrent diseases, history of concomitant drug use, exclusion of underlying liver disease

All follow-up information and procedures performed must be recorded as appropriate in the CRF.

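### The liver-injury table (SAP Table 2-9) counts central results only, so a higher local peak or a local-only bilirubin would be listed but not counted

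*SAP*

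**What the plan says.** **Source rule.** SAP 2.7.3 states: "For Hematology and Serum chemistry, central laboratory data will be included in the summary tables". It then says: "Local laboratory data will only be listed but not be included in the summary tables". Local values still reach the report as listings: "All laboratory data will be listed by participant and visit and if normal ranges are available abnormalities will be flagged".

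**Liver table.** The same section says that "newly occurring liver enzyme abnormalities will also be summarized based on the event criteria given in Table 2-9". Table 2-9 counts participants with ALT, or ALT or AST, above 3x, 5x, 8x, 10x and 20x ULN. It has further rows for TBL, ALP, combinations with TBL or INR, and potential Hy's Law. For threshold tables the SAP adds: "For notable summary tables, all post-baseline visits including unscheduled visits will be considered in the analysis". That sentence brings in unscheduled visits. It does not mention laboratory source.

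**Where local values come from.** Protocol 10.2.1 sends liver repeats to the central laboratory, then gives a fallback: "If results will not be available from the central laboratory, then the repeats can also be performed at a local laboratory". If a liver event is later reported, the associated local liver results are to be entered on the CRF. Protocol 8.4.1 covers participants who cannot visit the site under the public health emergency provisions of Section 4.6; for them "an alternative lab (local) collection may be used".

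**The concern.** Table 2-9 is meant to show how high liver tests went and how many participants reached each level. Protocol 10.2.1 collects local liver results because they belong to a reported liver event. The SAP's source rule then keeps those results out of the table designed to evaluate such events.

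Mixing laboratories is a good reason to keep local data out of mean changes by visit. It is a weaker reason here, because every Table 2-9 criterion except INR is a multiple of ULN, so a value can be read against its own laboratory's range.

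Safety is the primary objective, there is one arm, and about 70 participants are treated. Rows for the higher multiples and for potential Hy's Law may well be read as none versus one.

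**Working it through.** **1. Planning figures.** SAP section 3 gives about 100 screened, 30% screen failure and 15% dropout.
- Treated: 100 x (1 - 0.30) = 70.
- Completers: 70 x (1 - 0.15) = 59.5, about 60.

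Both agree with the SAP. I use n = 70 as the denominator.

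**2. Does any rule readmit local values to Table 2-9?**

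| Rule in SAP 2.7.3 | Effect on a local ALT, AST, TBL or ALP |
|---|---|
| Source rule for hematology and serum chemistry | Listed, not tabulated |
| Threshold-table rule | Adds unscheduled visits; silent on source |
| Table 2-9 text | Summarizes liver abnormalities; no exception on source |
| Urinalysis rule | Tabulates local data, but for urinalysis only |

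Nothing readmits them.

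**3. Two constructed cases** (values invented to show the mechanism).
- *Higher peak.* Central ALT is 1.0, 3.4 and 2.1 x ULN, with a local repeat of 6.2 x ULN. The central maximum is 3.4, so the participant counts as >3x only. With the local value the maximum is 6.2, so the participant also counts as >5x.
- *Potential Hy's Law.* Central ALT is 3.4 x ULN, no central TBL exceeds 2x ULN, one local TBL does, and ALP stays below 2x ULN. The SAP exempts this row from its same-timepoint requirement, so the local TBL could complete the criterion. Under the source rule it is not used. A later central TBL above 2x ULN would still complete the case.

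**4. Size.** SAP 5.4.1.2 gives the continuity-corrected score interval. With z = 1.96, z² = 3.84 and n = 70, the denominator is 2(n + z²) = 147.68. Here p is the proportion and q = 1 - p.

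- Upper limit: [2np + z² + 1 + z√(z² + 2 - 1/n + 4p(nq - 1))] / [2(n + z²)]
- Lower limit: [2np + z² - 1 - z√(z² - 2 - 1/n + 4p(nq + 1))] / [2(n + z²)], set to 0 when p = 0

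For 0/70: upper = (3.84 + 1 + 1.96 x √5.83) / 147.68 = 9.57 / 147.68 = 6.5%; lower = 0.

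For 1/70: upper = (2 + 3.84 + 1 + 1.96 x √9.71) / 147.68 = 12.95 / 147.68 = 8.8%; lower = (2 + 3.84 - 1 - 1.96 x √5.83) / 147.68 = 0.11 / 147.68 = 0.07%.

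| Participants qualifying only through local values (assumed) | Row as planned | Row with local values |
|---|---|---|
| 1 | 0/70: 0% (0 to 6.5%) | 1/70: 1.4% (0.07 to 8.8%) |
| 2 | 0/70: 0% (0 to 6.5%) | 2/70: 2.9% (0.5 to 10.9%) |
| 3 | 0/70: 0% (0 to 6.5%) | 3/70: 4.3% (1.1 to 12.8%) |

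Each such participant moves a row by 1/70 = 1.4 percentage points. The counts are assumptions, because the documents give no number of local liver tests.

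**The case against.** **Central testing is the default.** A reader might infer that urgent repeats of a rising liver test are mostly local. The documents do not support this. Protocol 10.2.1 directs repeats to the central laboratory, and both local routes are conditional. This objection stands, so frequency must be treated as unknown.

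**The first abnormal value is usually already in the table.** A repeat follows an initial trigger. On the default route that trigger is a central value and is counted, as are unscheduled central draws. This also stands. The loss is confined to rows that no central value reaches. The 0/70 versus 1/70 contrast applies only then, and its two intervals overlap almost entirely.

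**The information appears elsewhere.** Local values are listed, and flagged where ranges exist. Clinically significant abnormalities are recorded in the eCRF, and adverse events are tabulated by SOC, preferred term, severity and SMQ. So the values are not lost. None of these outputs gives a count of participants above a ULN multiple, so they are partial backstops.

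**Local collection is selective.** The CRF requirement in 10.2.1 depends on a reported liver event, so pooling would add event-driven data to systematic data. This carries little weight for Table 2-9, which counts whether a criterion was ever met and already takes event-driven unscheduled central values.

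**Programme consistency.** The SAP cites a master analysis plan and has been aligned with A2301 and A2302. Whether the source rule is programme-wide cannot be seen from these documents. Showing both versions of the table would preserve comparability.

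**Conclusion.** The point holds in a limited form. Applied as written, SAP 2.7.3 can undercount the higher rows of Table 2-9, or a potential Hy's Law case, when the decisive ALT, AST, TBL or ALP is local. Each affected participant is worth 1.4 percentage points of a row, taking n = 70 and assuming that no central value meets the same criterion. It is worth correcting, but nothing shows that it will occur often or at all.

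Three wider readings go beyond the documents:
- *Liver peaks are missed.* They are listed and may be reported as adverse events. What is missing is the count in the table.
- *The CTCAE tables need local data for the same reason.* The ULN-scaling argument does not reach Table 2-8 rows in absolute units, such as platelets, white cells, neutrophils, lymphocytes, cholesterol and triglycerides.
- *INR and the per-participant liver graphs are also excluded.* The rule names hematology and serum chemistry, while the protocol places INR in the coagulation panel. The graphs are not summary tables. For both, the source is unstated rather than excluded.

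**What to change.** Amend SAP 2.7.3 as follows.
- Keep by-visit summaries and the CTCAE tables central only.
- For Table 2-9, including potential Hy's Law, count CRF-recorded local ALT, AST, TBL and ALP as multiples of the local ULN, and local INR as reported, with a footnote identifying participants who qualify through a local value. Alternatively, add a with-local version beside the central-only table.
- State that the per-participant liver graphs, and the selection of participants for them, use the same data.

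The cost is SAP wording, some programming and capture of local reference ranges for the samples concerned. Participant procedures do not change. The drawback is that ULN scaling does not remove all assay differences between laboratories, which is why local values should stay identifiable.

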The assessment window is based on the study assessment schedule. The assessment schedule defined in the protocol is shown in Table 2-3. Note for Electrocardiogram (ECG), at Week 2, 12, 52 and SD visit pre and post dose assessments will be performed. ETD visit can be remapped to Week 24 only, and SD visit can be remapped to Week 2, 12 and 52.

| Visit name | BSL | Week 2 | Week 4 | Week 8 | Week 12 | Week 16 | Week 20 | Week 24 | Week 32 | Week 40 | Week 52 | ETD | SD |
|---|-----|----------------|--------|--------|----------------|---------|---------|---------|---------|---------|----------------|-----|----------------|
| Scheduled visit day | 1 | 15 | 29 | 57 | 85 | 113 | 141 | 169 | 225 | 281 | 365 | - | - |
| Vital signs Clinical chemistry* Hematology Urinalysis | x | x | x | x | x | x | x | x | x | x | x | x | x |
| Coagulation Panel | х | | x | | х | | | x | | x | x | x | x |
| | | | | | | | | | | | | | |
| Weight | | | | | x | | | | | | x | x | x |
| Electrocardiogram (ECG) | х | X ² | | | X ² | | | x | | | X ² | x | X ² |
| DLQI | Х | | Х | | Х | | | Х | | | Х | Х | Х |
| | | | | | | | | | | | | | |

| Table 2-3 | Assassment schedule |
|-----------|---------------------|
| Table Z-S | Assessment schedule |

X: to be recorded, BSL: Baseline, ETD: Early treatment discontinuation, SD: Study discontinuation ¹ only post baseline

² pre and post dose

* C-reactive protein (CRP), estimated Glomerular Filtration Rate (eGFR): assessed at screening, baseline, weeks 12, 24 and 52. Fasting glucose assessed at baseline, weeks 2, 12 and 52.

The Table 2-4 shows the assessment window for the assessments performed at every visits (i.e., vital signs, clinical chemistry, hematology, urinalysis).

If more than one assessment fall into the interval,

- Then if there is the scheduled visit recorded in eDiary or eCRF, this visit will be chosen.
- If no, the earliest visit day will be chosen.

| Novartis | Confidential | Page 26 of 54 |
|----------|--------------|------------------------|
| SAP | | Study No. CLOU064A1301 |

For example, when a participant discontinued study treatment after completing Week 2 and Week 4, and ETD visit occurred on Day 35 and SD visit occurred on Day 80, the ETD visit will be mapped to Week 8 and SD visit will be remapped to Week 12.

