If a participant visited the site earlier than scheduled visit day, e.g., Week 4 on Day 25 and ETD visit on Day 29, ETD visit will be remapped to Week 4. As the participant already performed Week 4 scheduled visit, the remapped Week 4 (ETD visit) will not be used.

If a participant visited the site late than scheduled visit day, e.g., Week 4 on Day 25, ETD visit on Day 58 and SD visit on Day 85, both ETD visit and SD visit will be remapped to Week 12. In this case, ETD visit will be used as Week 12, and Week 8 will be missing.

| Assessment visit | Scheduled visit Day | Assessment window |
|------------------|------------------------|--------------------|
| Week 2 | 15 | Day 2 to Day 15 |
| Week 4 | 29 | Day 16 to Day 29 |
| Week 8 | 57 | Day 30 to Day 57 |
| Week 12 | 85 | Day 58 to Day 85 |
| Week 16 | 113 | Day 86 to Day 113 |
| Week 20 | 141 | Day 114 to Day 141 |
| Week 24 | 169 | Day 142 to Day 169 |
| Week 32 | 225 | Day 170 to Day 225 |
| Week 40 | 281 | Day 226 to Day 281 |
| Week 52 | 365 | Day 282 to Day 365 |

Table 2-4Assessment window for vital signs, clinical chemistry, hematology,
urinalysis until Week 52

For the assessments which are not collected at every visit (e.g., DLQI etc.), assessment window will be combined. For example, DLQI is collected at Week 4, Week 12, Week 24 and Week 52. The assessment window will be combined as Table 2-5.

Table 2-5Assessment window for DLQI until Week 52

| Assessment visit | Scheduled visit day | Assessment window |
|------------------|------------------------|-------------------|
| Week 4 | 29 | Day 2 to Day 29 |

| Week 12 | 85 | Day 30 to Day 85 |
|---------|-----|--------------------|
| Week 24 | 169 | Day 86 to Day 169 |
| Week 52 | 365 | Day 170 to Day 365 |

Table 2-6 show the assessment windows of days for each assessment.

| | | | | - | | | | | | |
|---|--------|--------|--------|---------|---------|-------------|-------------|---------------------|-------------|-------------|
| Assessment visit | Week 2 | Week 4 | Week 8 | Week 12 | Week 16 | Week 20 | Week 24 | Week 32 | Week 40 | Week 52 |
| Scheduled visit day | 15 | 29 | 57 | 85 | 113 | 141 | 169 | 225 | 281 | 365 |
| Vital signs Clinical chemistry Hematology Urinalysis | 2-15 | 16-29 | 30-57 | 58-85 | 86-113 | 114- 141 | 142- 169 | 170- 225 | 226- 281 | 282- 365 |
| Coagulation Panel | 2-29 | | 30-85 | | 86-169 | | | 170-28 ⁻ | 1 | 282- 365 |
| | | | | | | | | | | |
| | | | | | | | | | | |

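### The SAP's rule for a worsening CTCAE laboratory abnormality compares values rather than grades when read literally, so chance variation inflates the count among participants abnormal at baseline

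*SAP*

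**What the plan says.** SAP 2.7.3 grades a list of laboratory parameters by CTCAE version 5.0 (Table 2-8) and announces the output: "The number and percentage of participants with CTCAE grade newly occurring or worsening after baseline will be presented". It then gives the case rule: "A case is considered as worsening abnormality if the value is notable at baseline and at least one post-baseline value is worse than baseline". The next display is described differently: "Shift tables will be provided on CTCAE grades to compare baseline relative to the worst grade". The note under Table 2-8 adds that "The comparison with baseline is not considered for derivation of LAB CTC grade", so each sample carries its own grade whatever the baseline was.

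On which samples count, SAP 2.7.3 says "For notable summary tables, all post-baseline visits including unscheduled visits will be considered in the analysis", and SAP 2.7 says "Safety summaries (tables, figures) include only data from the on-treatment period".

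The worsening sentence appears again, word for word, in the liver paragraph that introduces Table 2-9. That paragraph announces only newly occurring abnormalities and defines them by whether a criterion is met after baseline and not met, or missing, at baseline.

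**The concern.** The announced quantity is a change of grade, but the rule that produces it asks only for one worse value. ALT moving from 1.20 to 1.21 x ULN, or lymphocytes from 1400 to 1390/mm³, would each make a worsening case although the grade stays at 1.

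One baseline is set against many later samples, so ordinary fluctuation will often produce at least one worse value. The study has no control arm to show how large that background is. Safety is the primary objective, and a reader of the report could take the count as a laboratory signal.

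The undefined word notable adds a second uncertainty. Protocol Appendix 1 has its own notable hematology limits (hemoglobin below 10 g/dl, platelets below 75 000, leukocytes below 3 000, neutrophils below 1 500/mm³). In Table 2-8 those are the Grade 2 boundaries, not Grade 1. Two programmers could therefore build different tables from the same text.

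**Working it through.** The plan states no worsening rate, so there is no figure of its own to reproduce.

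**Inputs from the documents**
- Chemistry and hematology: SAP 2.1.1.4 treats these as "assessments performed at every visits (i.e., vital signs, clinical chemistry, hematology, urinalysis") and schedules them at Weeks 2, 4, 8, 12, 16, 20, 24, 32, 40 and 52, so k = 10. The follow-up visit is nominally Day 394. The on-treatment period ends at Day 365 + 28 = 393 if the last dose is on Day 365, so that visit is normally outside. If it falls inside, k = 11 and the shares below rise by about 2 points or less.
- Coagulation (INR): Weeks 4, 12, 24, 40 and 52, so k = 5.
- About 70 participants treated.
- Entry limits: ALT/AST up to 1.5 x ULN and INR up to 1.5 are allowed. No numeric limit is set for lymphocytes, triglycerides, cholesterol, CK, bilirubin or ALP. Grade 1 abnormalities at baseline are therefore possible.

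**Assumed, because the documents do not give them:** within-person correlation ρ and the share π abnormal at baseline.

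**Model.** No drug effect and no trend; standardized values with a normal random person effect; larger means worse. The cut-off is c = Φ⁻¹(1 − π). Given baseline x, the person mean M is normal with mean ρx and variance ρ(1 − ρ). Then

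P(no later value worse | x) = E[ Φ((x − M)/√(1 − ρ))^k ]

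P(flagged | abnormal baseline) = (1/π) ∫ from c to ∞ of φ(x) · {1 − E[ Φ((x − M)/√(1 − ρ))^k ]} dx

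| k | π | ρ = 0.3 | ρ = 0.5 | ρ = 0.7 | ρ = 0.85 |
|---|---|---|---|---|---|
| 10 | 2.5% | 30.7% | 44.7% | 59.5% | 71.6% |
| 10 | 5% | 40.9% | 52.9% | 65.0% | 74.8% |
| 10 | 20% | 66.2% | 71.3% | 76.8% | 81.6% |
| 5 | 2.5% | 18.9% | 30.9% | 45.3% | 58.6% |
| 5 | 5% | 26.6% | 38.0% | 50.8% | 62.1% |
| 5 | 20% | 49.5% | 56.5% | 63.8% | 70.3% |

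The simple figure k/(k + 1), which is 10/11 = 91% or 5/6 = 83%, does not apply. Participants picked for an abnormal baseline regress toward the mean, which lowers the share. The model also treats values as continuous. Coarse rounding, as may occur for INR, creates ties that do not count as worse and lowers the share further.

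**Value rule against grade rule, no drug effect, k = 10** (simulated lognormal variation, 15% dropout, entry limits applied for ALT and hemoglobin; variability assumed). Share of abnormal-baseline participants counted as worsened:
- ALT: 41% to 80% by value, 0% to 2% by grade
- Lymphocytes: 64% to 83% by value, 0% to 2% by grade
- Hemoglobin: 54% to 69% by value, 0% to 3% by grade
- Triglycerides: 73% to 82% by value, 5% to 24% by grade

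**Scale in 70 participants**
- ALT: about 0.3 to 6 abnormal at baseline; about 0.2 to 4 flagged by value and about 0 by grade.
- Triglycerides: about 12 to 18 abnormal; about 9 to 14 flagged by value and 0.5 to 4 by grade.
- Lymphocytes, a separate illustration with a normal distribution, mean 1800 and SD 500/mm³, ρ 0.6 to 0.8: Grade 1 is 800 to 1500, so the baseline share is Φ(−0.6) − Φ(−2) = 0.274 − 0.023 = 0.251, and 0.251 × 70 ≈ 18. Of these, 14 to 15 are flagged by value and 4 to 5 by grade. With a lognormal of the same mean and SD, the grade rule flags about 1.

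**The case against.** The best defence is context. The paragraph is about CTCAE grades, which are to be applied programmatically, and the sentence before the rule names the grade as the thing that worsens. A sensible programmer might read value as graded result. That stands to this extent: the text is ambiguous and does not force the literal reading. It does not remove the problem. The following sentence says grade where grade is meant, and the same rule is reused for Table 2-9, which holds xULN and INR thresholds and no grades.

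A reader might infer that most participants with an abnormal baseline will be reported as worsened. The documents do not support this as a general statement. With 10 samples and 2.5% abnormal, the share is below one half at correlations of 0.5 or less. With 5 samples it is lower still.

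A reader might also infer that the rule hides real grade worsening. It does not. The baseline-to-worst grade shift table will show every such change, and normal-range shift tables, maximum changes and full listings are planned too.

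The reach is limited as well. Only participants already abnormal at baseline are affected. The primary endpoint is treatment-emergent adverse events, and under Protocol 10.1.1 a laboratory value becomes one only if it causes signs or symptoms, is clinically significant or needs therapy. In Table 2-9 the ALT/AST criteria start above 3 x ULN while entry stops at 1.5 x ULN, so those rows are nearly unaffected.

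**Conclusion.** The point holds as a wording defect that can change reported counts. Under the literal rule and no drug effect, about 30% to 80% of participants abnormal at baseline would be flagged with 10 samples and about 20% to 70% with 5. These ranges rest on the assumed correlation (0.3 to 0.85), the assumed baseline prevalence (2.5% to 20%) and continuous measurement. In every parameter compared with 10 samples, the grade rule flagged far fewer; the gap was smallest for triglycerides.

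The practical result would be a worsening count that disagrees with the shift table in the same report, with no control arm to put it in proportion. For Table 2-9 the effect is mainly on the total bilirubin rows and possibly ALP. Severity is minor to moderate: the table is supportive and descriptive, and true grade shifts remain visible.

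**What to change.** In the CTCAE paragraph of SAP 2.7.3, define notable as CTCAE Grade 1 or higher, and define worsening as at least one post-baseline CTCAE grade higher than the baseline grade. The count then agrees with the shift table.

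In the liver paragraph before Table 2-9, delete the value-based worsening sentence. The table is announced as newly occurring only, and the criterion-met rule already defines that.

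The cost is two edits to the SAP text and a small programming change. No new data are needed.
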